Title: Effects of Osteopathic Manipulative Treatment and Bio Electro-Magnetic Regulation Therapy on Low Back Pain in Adults.

NCT04704375

June 13, 2019

Principal Investigator:

[name]., M.S., M.S. (Med Ed)
Lake Erie College of Osteopathic Medicine, Bradenton Florida
[contact]
Email: [contact]

Research Title:

Effects of Osteopathic Manipulative Treatment (OMT) and Bio Electro-Magnetic Regulation (BEMER) Therapy on low back pain in adults.

Research Purpose:

The aim of this project is to investigate the individual and combined effects of Osteopathic Manipulative Treatment (OMT) and Bio Electro-Magnetic Regulation (BEMER) Therapy on low back pain in adults.

Study Summary:

It is clear that low back pain (LBP) is a major challenge in our society, which can lead to severe disability in many individuals. Although there are several different treatments and approaches to help individuals with LBP, the number affected by this condition has been steadily increasing.

OMT has been shown to be helpful in the treatment of LBP. In fact, the use of OMT has been shown to increase mobility of the lumbar myofascial tissues, visceral motion and decrease pain in patients with LBP. Bio Electro-Magnetic Regulation (BEMER) Therapy is a therapeutic modality that deploys a biorhythmically defined stimulus through a Pulsed Electromagnetic Field (PEMF), which leads to an increase in blood flow. The positive effects of BEMER on the circulation has been shown to result in significant increases in arteriovenous oxygen difference, number of open capillaries, arteriolar and venular flow volume, and flow rate of red blood cells in the microvasculature [1, 2]. Therefore, BEMER can potentially be used in the treatment of LBP by improving microcirculation in muscular tissue. In fact, BEMER with physiotherapy showed reductions in pain and fatigue acutely in patients with chronic low back pain [3]. A systemic review of randomized controlled trials that investigated whether PEMF was effective in low back pain showed there was decrease in pain intensity and improved functionality in individuals with different low back pain conditions [4].

Therefore, it is plausible that the combination of OMT and BEMER therapy may help increase circulation to myofascial structures that influence low back restriction and pain. The purpose of

this study is to investigate the individual and combined effects of OMT and BEMER therapy on low back pain.

Review of Literature:

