1. BEMER is a therapeutic modality that deploys a biorhythmically defined stimulus through Pulsed Electromagnetic Field (PEMF). This stimulus has a targeted effect on the microvasculature, and the primary effect is an improvement in tissue microcirculation [3]. The positive effects of vasomotion on the microcirculation has been shown to result in significant increases in arteriovenous

oxygen difference, number of open capillaries, arteriolar and venular flow volume, and flow rate of red blood cells in the microvasculature [1, 2]. Therefore, BEMER can potentially be used in the treatment of LBP by improving microcirculation in muscular tissue.

- iii. Placebo (Light touch, and BEMER Sham): Treaters will place their hands lightly on the subject's lumbar paraspinal muscles in the supine and prone positions in the same area as where one would place your hands for lumbar MFR technique for the same amount of time as it would take to perform MFR in this area (approximately 5 minutes). However, no lifting or action will be done. In addition, the subject will lie down on the BEMER mat (as they would do during a BEMER session), but the device will not be activated. This treatment will be used as a control.
- e. The research assistants will individually coordinate experimental times with the subjects. A licensed osteopathic physician will be in the vicinity of the treatment location at all times while treatments are being given.
- f. OMT, BEMER, and placebo will be performed by osteopathic medical students who have completed additional training given by a licensed osteopathic physician to ensure uniform technique. A licensed osteopathic physician will be in the vicinity of the treatment location at all times while treatments are being given.
- g. All data collection logs will be de-identified of personal information and only contain the randomized participant ID number linking the participant to the data collected. [name], who is one of the research coordinators, will be the data analyst.
- h. The identifying information will be maintained by the principal investigator in a locked cabinet, which he alone has access to.

II. Study Procedures and Timeline

- a. Study duration

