 - i. The study duration is three weeks. The subjects will be required to have either OMT, BEMER, OMT+BEMER, or Placebo treatments during the course of the study. Each subject in the OMT groups (i.e. OMT and OMT+BEMER) will receive treatment 3 times per week for a period of 3 weeks. Subjects in the BEMER groups (i.e. BEMER and OMT+BEMER) will receive treatment 5 times per week for a period of 3 weeks. Finally, subjects in the Placebo group will receive the light touch and BEMER sham treatments at same intervals as the corresponding experimental groups. OMT, BEMER, and placebo treatments will be performed by osteopathic medical students who have completed additional training given by a licensed osteopathic physician, to ensure uniform technique.
- b. Recruitment:

- i. LECOM-Bradenton faculty, staff, osteopathic medical, dental, pharmacy, and master's students will be informed via email of the opportunity to participate in the research study and will be given contact information to confirm eligibility with a study coordinator (Appendix A).

c. Experimental Sessions

- i. Following written consent (Appendix B), subjects will be given a randomized study ID number. They will be randomized into their treatment group.
- ii. Each subject in the OMT groups (i.e. OMT and OMT+BEMER) will receive treatment 3 times per week for a period of 3 weeks. As previously mentioned, subjects in the BEMER groups (i.e. BEMER and OMT+BEMER) will receive treatment 5 times per week for a period of 3 weeks. Finally, subjects in the Placebo group will receive the light touch and BEMER sham treatments at same intervals as the corresponding experimental groups. OMT, BEMER, and placebo treatments will be performed by osteopathic medical students who have completed additional training given by a licensed osteopathic physician, to ensure uniform technique. All treatments will be performed during the span of three consecutive weeks.
- iii. Subjects will complete brief questionnaires regarding low back pain and quality of life before the beginning of study and will complete the same questionnaires following the completion of the three week treatment (Appendices C, D, E).

III. Analysis

a. Study Statistics

- i. Primary outcome variable
 1. Questionnaire ratings before and after treatments
- ii. Statistical plan including sample size justification and interim data analysis
 1. Paired T-tests (N~10 subjects) to investigate the changes in low back pain after each treatment protocol.

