 2. One-Way ANOVA to investigate any statistically significant differences between the means of each of the 4 experimental groups.
- iii. Early stopping rules
 1. Any adverse effect, as determined by the attending licensed osteopathic physician. No adverse effects are anticipated.

b. Blinding

- i. All outcome analyses will be performed in a blinded fashion. Subject survey and corresponding data will be de-identified and analyzed retrospectively by investigators with no exposure to the treatment sessions. Doing so will eliminate bias associated with investigator self-interest and ensure subject anonymity.

IV. Drugs/Substances/Devices

- a. Drugs will not be used in this trial. Instead, subjects will be given osteopathic manipulative treatment, BEMER therapy, and placebo light touch.
- b. The device utilized is BEMER Pro set.

Research Participants

The target population is LECOM-Bradenton faculty, staff, osteopathic medical, dental, pharmacy, and master's students who are currently experiencing low back pain. The study will not target participants from a vulnerable or at-risk population. Our target population will be informed via email of the opportunity to participate in the research study and will be given contact information to confirm eligibility with a study coordinator.

I. Inclusion

- a. LECOM-Bradenton faculty, staff and Students currently enrolled in LECOM-Bradenton's osteopathic medical program, pharmacy program, dental program, and master's program who are currently experiencing low back pain will be approached for recruitment.

II. Exclusion

- a. Subjects will be excluded if they are unable to provide informed consent, are currently pregnant, or have a known medical history of current
 - i. Psychiatric conditions
 - ii. Skin disorders or open wounds precluding skin contact
 - iii. Fasciitis or fascial tears
 - iv. Myositis
 - v. Neurological symptoms such as numbness, tingling, weakness in lower extremities
 - vi. Neoplasia
 - vii. Cancer
 - viii. Bone fracture, osteomyelitis, or osteoporosis
 - ix. Coagulation problem
 - x. Deep vein thrombosis
 - xi. Adrenal diseases/syndromes
 - xii. Acute upper or lower respiratory infection
 - xiii. Immunosuppressive syndromes
 - xiv. Radiation or chemotherapy within the past 3 years
 - xv. Lupus
 - xvi. Osteopenia
 - xvii. Congestive heart failure
 - xviii. BMI greater than 30
 - xix. Any other autoimmune disease not stated above
 - xx. Medication changes within the last 4 weeks

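### The only between-arm test is an omnibus one-way ANOVA with no pre-specified contrasts, score form or baseline adjustment, so the planned analysis does not answer the question about OMT, BEMER and their combination.

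*Combined protocol and SAP*

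**What the plan says.** The aim appears under Research Purpose: "investigate the individual and combined effects of Osteopathic Manipulative Treatment (OMT) and Bio Electro-Magnetic Regulation (BEMER) Therapy on low back pain in adults". Subjects are randomised to OMT, BEMER, OMT+BEMER or Placebo (Methodology, I.c.iii), and Placebo is designated the control (I.d.iii).

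The statistical plan (Methodology, III.a.ii) has two items. Item 1 works within each arm and is worded "Paired T-tests (N~10 subjects) to investigate the changes in low back pain after each treatment protocol". Item 2 is the sole comparison across arms, and its full wording is "One-Way ANOVA to investigate any statistically significant differences between the means of each of the 4 experimental groups".

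The primary outcome (III.a.i) is "Questionnaire ratings before and after treatments". Three instruments are collected: SF-12, a pain VAS and the Oswestry questionnaire (Appendices C, D and E). Baseline values will exist for all of them: "Subjects will complete brief questionnaires regarding low back pain and quality of life before the beginning of study" (II.c.iii), and the same forms are repeated after the three weeks of treatment.

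No pairwise or post-hoc comparison, factorial term, multiplicity rule or baseline covariate is mentioned.

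**The concern.** The aim calls for specific differences: each treatment against control, and the combination against control and against each component. The F test addresses only the hypothesis that all four means are equal. Rejecting it says that some arm differs, not which one or in what direction. The paired tests look within each arm and make no use of the Placebo arm.

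Followed exactly, then, the plan yields no stated estimate of OMT, BEMER or OMT+BEMER against Placebo. Those comparisons would be picked once the data are in, without error control. The open choice between final and change scores adds a second decision that can be made after seeing results. Separately, the baseline score is collected but left out of the between-arm model, which costs precision in a trial that has little to spare.

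**Working it through.** **Inputs from the documents.** Four arms; about 10 subjects per paired test (III.a.ii.1); a budget for 40 subjects (Payment and Costs, II.a.ii). 4 × 10 = 40, so these agree. The figure of 10 cannot be reproduced further, because no alpha, power, effect size or SD is given.

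**Assumptions.** Two-sided alpha 0.05, equal allocation, 10 complete subjects per arm, equal SD before and after treatment (SD = 1), effect 0.8 SD, and pre-post correlation r from 0.3 to 0.8.

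**1. What the F test can distinguish.** Order the arms Placebo, OMT, BEMER, OMT+BEMER. If only OMT works, the means are (0, 0.8, 0, 0.8). The noncentrality is 10 × 4 × 0.4² = 6.4, and with 3 and 36 df the power is 0.50 on final scores. If only BEMER works, the means are (0, 0, 0.8, 0.8), with the same noncentrality and the same power. On change scores at r = 0.6 the noncentrality is 6.4/0.8 = 8.0 and power is 0.60, again identical for the two cases.

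**2. Whether the paired tests fill the gap.** Suppose all four arms improve equally, by dz within-subject SDs, so that there is no treatment effect. The power p of each paired test comes from the noncentral t with 9 df and noncentrality dz × √10. The chance that at least one active arm is significant while Placebo is not is (1 − (1 − p)³)(1 − p).

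| dz | p | chance |
|---|---|---|
| 0.4 | 0.21 | 0.40 |
| 0.6 | 0.40 | 0.47 |
| 0.8 | 0.62 | 0.36 |
| 1.0 | 0.80 | 0.20 |

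**3. Precision of the three possible responses.** The variance factors are 1 for final scores, 2(1 − r) for change scores, and (1 − r²)(1 + 1/34) for ANCOVA, where 1/34 is the expected cost of estimating the slope. At r = 0.6 these are 1, 0.80 and 0.64 × 35/34 = 0.659. ANCOVA is then worth 1/0.659 − 1 = 52% more subjects than final scores and 0.80/0.659 − 1 = 21% more than change scores.

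The standard error of a difference between two arms is √(factor × 2/10), which at r = 0.6 is 0.447, 0.400 and 0.363. The difference detectable with 80% power is about 2.88 standard errors (36 df, or 35 for ANCOVA).

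| r | ANCOVA gain v final | ANCOVA gain v change | Detectable, final | Detectable, change | Detectable, ANCOVA |
|---|---|---|---|---|---|
| 0.3 | 7% | 49% | 1.29 SD | 1.52 SD | 1.25 SD |
| 0.5 | 30% | 30% | 1.29 SD | 1.29 SD | 1.13 SD |
| 0.6 | 52% | 21% | 1.29 SD | 1.15 SD | 1.05 SD |
| 0.7 | 90% | 14% | 1.29 SD | 1.00 SD | 0.93 SD |
| 0.8 | 170% | 8% | 1.29 SD | 0.81 SD | 0.78 SD |

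**4. Power of a named contrast.** For OMT v Placebo at 0.8 SD and r = 0.6, unadjusted power is 41% (final), 49% (change) and 57% (ANCOVA). With Holm over the three Placebo contrasts it is 27%, 34% and 42%, from 40,000 simulated trials with means (0, 0.8, 0, 0.8). If only the OMT arm differs, the ANCOVA figure is 39%.

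**5. Interaction.** Its standard error under ANCOVA at r = 0.6 is √(0.659 × 4/10) = 0.513, so 80% power needs 2.88 × 0.513 = 1.48 SD.

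**The case against.** The strongest reply is that the defect is one of pre-specification rather than of the model. A one-way ANOVA contains the four means, pairwise follow-up is a common next step, and item 1's reference to changes in pain suggests that change scores are meant. This is fair as far as it goes, but neither the follow-up nor the score form is written down, and nothing controls error across the comparisons.

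Three narrower points stand:

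- Only the missing contrasts bear on attribution. The missing covariate affects precision and chance imbalance.
- The precision gain is conditional. By the formula above, ANCOVA loses slightly to final scores below r of about 0.17 and to change scores above about 0.94. If change scores were intended, the gain at r = 0.6 to 0.8 is 21% falling to 8%.
- Contrasts against Placebo are not the most powerful choice. With no interaction, a pooled OMT main effect at 0.8 SD and r = 0.6 has about 86% power under ANCOVA, unadjusted, against 57% for OMT v Placebo (42% after Holm).

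The reason for not relying on the pooled effect lies in the design. Sham procedures are described only for the control: "subjects in the Placebo group will receive the light touch and BEMER sham treatments at same intervals as the corresponding experimental groups" (II.a.i). The single-treatment arms are not said to receive the sham of the other treatment, so the four arms may not form a clean 2 × 2. A sponsor who confirmed that they do could reasonably choose otherwise.

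**Conclusion.** The concern holds. No planned analysis compares OMT, BEMER or the combination with Placebo, and the omnibus F behaves identically under opposite explanations (50% power at 0.8 SD on final scores in both). Reading significance arm by arm from the paired tests would mislead in 20% to 47% of trials with no true difference between arms, over the range of common improvement assumed. Baseline adjustment would add the equivalent of 7% to 170% more subjects over final scores, or 49% down to 8% over change scores, for r from 0.3 to 0.8.

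The attribution failure follows from the text alone. The sizes rest on assumed alpha, effect, r and equal allocation, since the documents give none. Ten complete subjects per arm is a best case, because subjects who do not adhere or who have adverse effects are removed (Research Participants, III). The change improves interpretability and precision; it does not make the sample size adequate.

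**What to change.** Replace item III.a.ii.2 with an ANCOVA of the post-treatment score on arm (four levels) and the pre-treatment value of the same score.

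- **Response.** Name one questionnaire as primary in advance. The VAS in Appendix D is the natural candidate because it measures pain itself. Analyse the others with the same model as secondary, reporting estimates and confidence intervals only.
- **Primary contrasts.** OMT v Placebo, BEMER v Placebo and OMT+BEMER v Placebo, Holm-adjusted at two-sided 0.05.
- **Combination against components.** Report OMT+BEMER v OMT and OMT+BEMER v BEMER as estimates with 95% confidence intervals.
- **Interaction and pooled main effects.** Label these exploratory, given the uncertainty about sham in the single-treatment arms and the size of interaction that could be detected.
- **Paired changes.** Keep the within-arm pre-post changes as description, without inference about treatment.

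The cost is revised wording, the choice of one primary questionnaire and one degree of freedom for the baseline covariate. No additional subjects, visits or data are needed.

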Low back pain (LBP) has become a major challenge in our society and has a relatively high incidence and prevalence [5]. Moreover, LBP currently affects people of all ages and is a leading contributor to disease burden worldwide [6]. Individuals affected by LBP may experience this discomfort and associated disability for several months, and a proportion may remain severely disabled [7]. For nearly all people with low back pain, it is not possible to identify a specific nociceptive cause. Most people with new episodes of LBP may recover quickly; however, recurrence is common and in many cases, LBP becomes persistent and disabling [8].

Despite the overabundance of treatments and approaches devoted to LBP, this back related disability and the number of individuals affected have steadily been increasing [9, 10]. During the past three decades, changes have been made to key recommendations in national clinical practice guidelines. In fact, currently there is a bigger emphasis placed on self-management, physical and psychological therapies, and some forms of complementary medicine (such as spinal manipulation, massage, acupuncture), and less emphasis on pharmacological and surgical treatments [11].

Despite multiple clinical guidelines providing similar recommendations for managing low back pain, a substantial gap between evidence and practice exists [12]. Osteopathic manipulative treatment (OMT) is a distinctive modality used by osteopathic physicians to complement conventional management of LBP. There is considerable variability in OMT approaches when treating for LBP. Furthermore, osteopathic physicians combine conventional and complementary treatments when caring for patients with LBP. This increased variability in the approach to care for LBP patients requires more empirical data to determine the best approaches to treat LBP [13]. Franke *et al.* [14] conducted a meta-analysis that investigated the effect of OMT in LBP. The authors reported that some studies observed significant effect of OMT on pain [15-17], whereas other reported either a non-significant effect [18-20], or an effect in favor of the control treatment [19, 20]. It is clear that more research to better describe the effects of OMT on LBP is warranted.

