 - xxi. Asthma exacerbations within the last 4 weeks
 - xxii. Immunosuppressive therapy as a consequence of organ transplantation
 - xxiii. Immunosuppressive therapy as a consequence of allogeneic cellular transplants or bone marrow stem cell transplantation

- xxiv. Other conditions often requiring immunosuppressive therapy
- xxv. Anticoagulant therapy
- xxvi. Known sensitivity to the carotid sinus reflex
- b. Subjects will be screened for eligibility based on the inclusion and exclusion criteria described above at the point of subject consent. No protected health information will be collected from subjects who are not eligible to participate in the study.
- c. If subjects develop any of the above issues during the course of the study, they will be removed from the study without penalty and will still receive compensation.

III. Definition of treatment failure or subject removal criteria

- a. Subjects who do not adhere to the full treatment regimen will be removed from the study.
- b. Subjects who experience any adverse effects from treatment, as determined by a licensed osteopathic physician, will be immediately removed from the study. However, we do not anticipate any adverse effects during the study.

Risks and Benefits

I. Risks

- a. Anticipated medical risks**
 - i. After OMT, muscle tenderness and generalized discomfort may be noted 24-48 hours after treatment in a small number of patients.
 - ii. There is little empiric data about the “hazards” to patients of student-performed procedures. Further, this study does not employ any inherently forceful techniques.
 - iii. There are no anticipated adverse effects associated with BEMER therapy.
- b. Steps taken to minimize the risks**
 - i. All Osteopathic Medical students performing osteopathic manipulation will receive additional special training by a licensed osteopathic physician, member of the LECOM-Bradenton OMM Department, and will disclose their true identity to the subjects to avoid any misconceptions that they are licensed physicians. Student-treaters will be critiqued by a physician until they are approved to perform OMT on the subjects.
 - ii. A licensed osteopathic physician will be in the vicinity of the treatment location at all times a treatment is being given.

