 - iii. The operation of the BEMER Pro Set will be done by students, who will be trained by a BEMER representative. The BEMER representative will ensure students are well trained in the operation of the device. In addition, the Principal Investigator will also be available during the training and throughout the study duration to assist the students.
 - iv. There are no funds designated to compensate subjects for injury. The principal investigator will work with injured subjects to provide them with further information to the best of his ability.

c. Plan for reporting adverse events

- i. All serious or unanticipated adverse events must be reported to the LECOM IRB promptly.
- ii. All protocol amendments will be submitted to IRB for approval, with the exception of changes that must be made in order to eliminate any imminent risk of harm to subjects or to others. In this circumstance, the investigator will act to eliminate the immediate risk but must subsequently submit an appropriate protocol amendment and await approval before proceeding with the revised protocol.

II. Benefits

a. Description of probable benefits

- i. Subjects may experience a decrease in low back pain. This can translate to healthy and natural ways to improve quality of living in patients with disabling low back pain. Individually, patients could see significant increases in quality of life.
- ii. With regards to society, this study could provide patients with an efficient and inexpensive way to alleviate many of the disabilities that are associated with living with low back pain.

Consent Process and Privacy Protection

I. Consent Process

- a. Participants will be introduced to the study through classroom announcements and recruitment emails. If they decide to participate we will provide participants with a written informed consent form (Appendix B) for them to read. In addition, a researcher will thoroughly explain the study to them to ensure that the subject is willing to participate in the experiment. The participant will then sign the form after comprehension is assessed via verbal reiteration and opportunity has been provided for questions.

II. Privacy Protection/Confidentiality

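### Entry requires only current low back pain, and episode duration is neither recorded nor used in randomisation or analysis, which costs precision between arms and leaves the within-arm tests open to natural recovery

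*Combined protocol and SAP*

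**What the plan says.** **Entry.** Under Research Participants, I. Inclusion, faculty, staff and students "who are currently experiencing low back pain will be approached for recruitment". None of the 26 exclusions (II.a, i to xxvi) concerns episode duration or pain severity. The closest is "Neurological symptoms such as numbness, tingling, weakness in lower extremities", which concerns leg symptoms. Screening uses these lists only: "Subjects will be screened for eligibility based on the inclusion and exclusion criteria described above at the point of subject consent". The recruitment email (Appendix A) adds no further limit.

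**Natural course.** The Review of Literature states: "Most people with new episodes of LBP may recover quickly; however, recurrence is common and in many cases, LBP becomes persistent and disabling".

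**Timing.** Study Procedures and Timeline says "The study duration is three weeks". Questionnaires are completed once beforehand, and subjects "will complete the same questionnaires following the completion of the three week treatment".

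**Randomisation and analysis.** Subjects are randomised to OMT, BEMER, OMT+BEMER or placebo (Study Design, c.iii). No stratification factor is named. The Analysis section plans paired t-tests within each treatment protocol (N~10) and a one-way ANOVA across the four groups, with no covariate. The budget is for about 40 subjects.

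**The concern.** The protocol describes two different courses of back pain, one often short and one persistent, and admits both without recording which a subject has. A three-week window with one reading before and one after is short enough for spontaneous recovery to make up part of the measured change.

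Two things are at stake. In the between-arm comparison, a mixture of fast and slow improvers widens the spread of change scores and lets arms of 10 differ by chance in their share of new episodes. In the within-arm paired t-tests, natural recovery is counted as treatment response, because those tests have no control. Baseline VAS does not fill the gap: a new and a persistent case can start from the same score.

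**Working it through.** **Inputs from the protocol.** Four arms, about 40 subjects, N~10 per paired test. The only figure that can be checked is 40 / 4 = 10 per arm, which agrees. No alpha, power, SD or effect size is stated, so N~10 itself cannot be reproduced. With an assumed two-sided 5% level, 10 per arm gives 80% power for one arm against placebo only at a standardised difference of 1.32, so there is little precision to spare.

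**Assumptions (not in the documents).** Share of new episodes p = 20-50%. Extra three-week improvement of new over persistent episodes g = 10-20 mm on the 100 mm VAS.

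**1. Chance imbalance between two arms of 10.** The SD of the resulting difference in mean change is g × √(2p(1−p)/10).

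| p | g (mm) | SD (mm) | 95% range (±1.96 SD) |
|---|---|---|---|
| 0.2 | 10 | 10 × √0.032 = 1.79 | ±3.5 mm |
| 0.2 | 20 | 20 × √0.032 = 3.58 | ±7.0 mm |
| 0.5 | 10 | 10 × √0.050 = 2.24 | ±4.4 mm |
| 0.5 | 20 | 20 × √0.050 = 4.47 | ±8.8 mm |

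From two binomial(10, p) counts, two given arms differ by 2 or more new episodes with probability 0.39 (p = 0.2) to 0.50 (p = 0.5).

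**2. How much this adds to ordinary sampling error.** Assume an SD of change of 15 mm within each type of episode. With perfect balance the 95% range of a two-arm difference is 1.96 × 15 × √(2/10) = ±13.1 mm. Adding the imbalance variance gives 1.96 × √(45 + 3.2) = ±13.6 mm at the mildest corner and 1.96 × √(45 + 20) = ±15.8 mm at the worst.

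**3. Simulation of the planned tests.** Four arms of 10, analysed as change in VAS. Assumed: baseline mean 35 mm, SD 20; noise SD 12; each new episode loses 60% of its pain; scores clipped at 0 and 100.

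- *No treatment effect.* With 0%, 25%, 50% and 75% new episodes, the within-arm paired t-test is significant in 5%, 9%, 32% and 66% of trials. The ANOVA stays at 4.6-5.5% throughout.
- *True effect of 15 mm in every active arm.* Going from no new episodes to 50% raises the SD of change from 11.2 to 17.1 mm. ANOVA power falls from about 0.72 to about 0.3 (0.28-0.31 over separate runs).
- *Onset stratum used.* At 50% new episodes, including the stratum in the model raises power from about 0.3 to about 0.4 (0.39-0.44 over separate runs). With no new episodes, an uninformative extra factor costs almost nothing (0.72 to 0.71).
- *Stratified but not adjusted.* With perfect balance at 50% new episodes and the stratum left out of the model, the ANOVA rejects in only 0.7% of trials with no effect, and power drops to 0.21. Stratification and adjustment therefore have to come together.

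**The case against.** The strongest defence is that the trial is randomised with a placebo arm. Natural recovery falls on all four arms alike in expectation, and the ANOVA keeps its 5% level whatever the mix. This stands. A reader might infer that self-resolving episodes could create a spurious difference between treatment and placebo beyond the nominal error rate, and the plan does not support that reading.

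A broad population is also a legitimate choice, and the target is stated simply as adults with current low back pain. The benefits section hopes for carry-over: "This can translate to healthy and natural ways to improve quality of living in patients with disabling low back pain". It does not define the trial population as disabling pain, so there is no contradiction with the entry rule. What does not follow is that duration can go unrecorded: broad entry is compatible with stratifying on it.

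Two further inferences go too far. One is that new episodes would be pain-free by week 3 and so carry almost no information. The protocol says only "Most people with new episodes of LBP may recover quickly", with no time frame, and its background counts a trial in acute low back pain among the studies showing an OMT effect. The other is that imbalance could move arm means by as much as a treatment effect. The worst range here, ±8.8 mm, is below the 15 mm effect used in the illustration, and the small sample contributes more to the uncertainty than the imbalance does.

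A reader might also want a minimum VAS score at entry, to avoid a floor at zero. The documents do not show that low scores would be common, and the trade-off is poor. If baseline VAS has mean 20-40 mm and SD 15-20 (assumed, truncated at 0), a 30 mm minimum would turn away about 25-72% of volunteers at a single campus. It would narrow the stated population, and selecting on the outcome scale adds regression to the mean. With assumed reading noise of 7-10 mm and no true change, that alone raises paired-test false positives from 5% to about 6-28%.

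**Conclusion.** The point holds as a loss of precision between arms and as a limit on what the paired t-tests can show. It is not a bias in the placebo-controlled comparison. Under the assumed 20-50% new episodes improving 10-20 mm more, imbalance alone contributes ±3.5 to ±8.8 mm to a two-arm difference. In the simulated case with half new episodes, ANOVA power for a 15 mm effect falls from about 0.72 to about 0.3, and about 0.1 of that is recoverable by using onset. Under the same mix, a paired t-test is significant in about a third of trials with no treatment effect.

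The direction follows from the protocol's own account of natural course. The sizes rest on assumptions about mix, recovery and spread that the documents do not give, and they cover only the VAS, whereas the outcome also includes the SF-12 and Oswestry questionnaires. The plan permits new episodes; it does not say how many would enter.

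**What to change.** 1. At the eligibility check, before randomisation, ask and record time since onset of the current episode.
2. Stratify randomisation on it, for example under 12 weeks versus 12 weeks or longer; the cut-off is the sponsor's to choose. Use concealed blocks of varying size: the student treaters know what they deliver, and fixed small blocks could make the next assignment guessable.
3. Include the stratum as a factor in the between-arm comparison. Stratifying without adjusting makes the test conservative.
4. State that conclusions about treatment effect rest on the between-arm comparison with placebo. Report the paired t-tests as descriptive only.

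The cost is one extra question, two randomisation lists and one model degree of freedom (error df 36 to 35 with 40 subjects). Incomplete blocks may leave a small residual imbalance. The entry criteria and the target of about 40 do not change, and no minimum VAS score is needed.
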